9.2 Sample Size Determination

Approximately 120 participants will be screened/enrolled to achieve 100 evaluable participants.

Note: “Enrolled” means a participant’s, or their legally acceptable representative’s, agreement to participate in a clinical study following completion of the informed consent process. Potential participants who are screened for the purpose of determining eligibility for the study, can be rescreened once. If they are not subsequently assigned to receive AZD7442 in the study, they are considered “screen failures”.

The total sample size of 100 participants across all pediatric age groups is the minimum number required to adequately characterize the AZD7442 safety profile in pediatric participants following IM or IV administration (based on FDA feedback). Furthermore, preliminary PK simulations based on adult PK data determined that with a minimum sample size of 24 participants ($n = 6$, per route of administration, in the 4 age groups from any cohort), and the proposed PK sampling scheme, 80% of the simulated trials estimated the geometric mean for CL with a 95% confidence interval that remained within 60% to 140% of the point estimate in each pediatric subgroup.

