## 2 CHANGES TO PROTOCOL PLANNED ANALYSES

A summary of adverse events by maximum intensity was planned in protocol Section 9.4.4. This was removed per AZD7442 program-level data presentation decision.

Enrolment into the study has been discontinued due to FDA feedback. No participant has been included for Cohort 3, and the full analysis set will contain 46 instead of 100 participants. Planned analyses for Cohorts with no participants will not be conducted.

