#### **4.1.2.2 Presentation**

Participant disposition will be summarized and will include the following information: number of participants screened, randomized and dosed, number and percentage of participants completing the study and the number and percentage of participants who were withdrawn (including primary reason for withdrawal). The summary will be done overall and by cohort.

Participant discontinuations will be listed including the date of study exit, duration of participation and primary reason for discontinuation.

Participants and/or data excluded from the PK analysis set (see Section 4.1.1) will be listed including the reason for exclusion.

The analysis set to be used for these summaries and listings is the SPS (see Section 4.1.1).

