#### 4.2.1 Primary PK Endpoints

To evaluate the serum concentrations of AZD7442 after a single IM or IV dose in pediatric participants, the primary PK endpoints serum AZD7442 concentrations and PK parameters derived from these by non-compartmental analysis in accordance with AstraZeneca Pharmacokinetic Evaluations in Clinical Trials guideline will be listed and presented separately in tabular and graphical form.

Any serum concentrations for AZD7442 will be reported as the individual component concentrations AZD8895 and AZD1061 as well as the sum of the two individual component concentrations labelled as AZD7442.

The analysis of these endpoints will comprise of descriptive summary statistics stratified by cohort, route of administration (IM or IV) and weight categories (1, 2, 3, 4 and all).

For PK parameters other than *tmax* and *tlast*, the following descriptive statistics will be presented: *n*, gmean, gSD, 95% CI for the gmean, gCV, arithmetic mean, arithmetic SD, median, minimum, and maximum. For *tmax* and *tlast*, only *n*, median, minimum, and maximum will be presented.

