### **Analysis of Adverse Events**

The safety of AZD7442 will primarily be assessed by:

- Incidence of TEAEs through end of study
- Incidence of SAEs through end of study
- Incidence of AESIs through end of study

Summaries of these incidences will include the number and percentage of participants reporting at least one event with the 95% exact Clopper-Pearson confidence interval for the percentage, number of events, exposure adjusted rates and presented by cohort and route of administration.

An overview of AEs will be presented for each cohort and route of administration, including the number and percentage of participants with any AE and SAEs. Summaries will present the relationship to IMP as assessed by the Investigator, seriousness, and deaths.

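### SAP 4.2.2.1 names no all-participants row for TEAE, SAE and AESI incidence, although the safety sample size rests on the total across all children

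*SAP*

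**What the plan says.** SAP 4.2.2.1 (Analysis of Adverse Events) makes the incidences of TEAEs, SAEs and AESIs the primary way of assessing safety. Each summary gives the number and percentage of participants with an event, the "95% exact Clopper-Pearson confidence interval for the percentage", and then "number of events, exposure adjusted rates and presented by cohort and route of administration". The next paragraph uses the same layout: "An overview of AEs will be presented for each cohort and route of administration". Neither sentence mentions a total.

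Protocol 9.2 justifies the safety sample size on the study total: "The total sample size of 100 participants across all pediatric age groups is the minimum number required to adequately characterize the AZD7442 safety profile". SAP section 2 reports that enrolment stopped early, so that "the full analysis set will contain 46 instead of 100 participants", and that "No participant has been included for Cohort 3". That leaves at most four cohort-by-route cells: Cohorts 1 and 2, each IM and IV.

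Where the SAP wants a study-level view of disposition, it says so (SAP 4.1.2.2): "The summary will be done overall and by cohort".

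Two further passages bear on the remedy. SAP 4.2.2 bases the summaries of primary safety endpoints on the SES, the set that needs a quantifiable post-dose neutralizing titer. SAP Table 2 assigns the same endpoints to the SAF. Protocol 8.1.1 has COVID-19 qualifying symptoms recorded as adverse events in Cohort 1. In Cohorts 2 and 3 they are recorded only if serious, if they lead to study discontinuation, or if judged not related to COVID-19.

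**The concern.** Safety is a co-primary objective, and the protocol argues for the sample size on all children together. The tables specified for its leading measures split those children into up to four cells and name no combined estimate. With 46 participants instead of 100, precision is already scarce.

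The counts in separate cells can be added by hand. The exact interval cannot be read off the cell intervals, and the SAP plans no pooled one. The loss is greatest for rare events such as SAEs and AESIs. There the useful statement is often how high the true rate could still be when few or no cases were seen.

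Dose gives no reason to show Cohorts 1 and 2 only separately: protocol Table 6 plans the same dose for both within each weight band and route.

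**Working it through.** The documents give no interval width, detectable rate or cell size for adverse events, so there is no stated figure to reproduce.

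**Inputs**
- Participants: 46 in the full analysis set (SAP section 2). The SAF has the same rule of having received study drug (SAP Table 1), so it is also 46.
- Occupied cells: at most four, because Cohort 3 is empty.
- Interval: 95% Clopper-Pearson, read as two-sided.
- Cell sizes: not given, so treated as a range.

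**Formula.** With 0 events in n participants, the upper limit is 1 − 0.025^(1/n).

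| n | Zero-event upper limit | Interval with 1 event |
|---|---|---|
| 46 (all) | 1 − 0.025^(1/46) = 7.7% | 0.1% to 11.5% |
| 23 | 1 − 0.025^(1/23) = 14.8% | 0.1% to 21.9% |
| 12 | 1 − 0.025^(1/12) = 26.5% | 0.2% to 38.5% |
| 11 | 1 − 0.025^(1/11) = 28.5% | 0.2% to 41.3% |
| 6 | 1 − 0.025^(1/6) = 45.9% | 0.4% to 64.1% |

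For comparison, the planned 100 would have given 3.6%.

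**What follows without assuming a split.** If all four cells are occupied, the mean is 46/4 = 11.5 per cell. The smallest cell then holds at most 11 children, and its zero-event limit is at least 28.5%. The most uneven split is 43/1/1/1. The largest cell then has a limit of 8.2%, still above the pooled 7.7%, and each single-child cell has 97.5%.

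**What follows under an assumed split**
- *Nearly all in Cohort 1, evenly by route:* two cells of 46/2 = 23, each with a limit of 14.8%, nearly twice the pooled figure.
- *In proportion to the protocol Table 5 minima* of 19, 12, 14 and 7 (sum 52): 46 × 19/52 = 16.8, 46 × 12/52 = 10.6, 46 × 14/52 = 12.4 and 46 × 7/52 = 6.2. Cells of about 17, 11, 12 and 6 have limits of 19.5%, 28.5%, 26.5% and 45.9%. This is an illustration only, because it ignores the 32 any-cohort places in Table 5.

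**Which analysis set reaches 46.** Protocol Table 2 schedules no neutralizing antibody sample for neonates, and protocol 8.5.1 limits their blood samples to safety and PK. A neonate therefore cannot meet the SES titer rule. A total row on the SES would lose any neonates dosed, and anyone else without a quantifiable post-dose titer. Only the SAF gives 46.

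**The case against.** **A total may already be planned.** SAP 4.2.2.1 does not exclude one, and SAP 3.3.1 leaves presentation details to a table shells document outside the protocol and SAP. Protocol 9.4.4 presents adverse events by treatment group, and the synopsis describes one arm, so a single group is a possible reading. This stands against any claim that a pooled result will never appear. It does not remove the need to specify the main estimate of a co-primary objective in the SAP.

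**A reader might infer that no safety result uses all the children.** The documents do not support that. As written, the vital signs summaries (SAP 4.2.2.3), the ECG shift table (SAP 4.2.2.5) and the summary of cardiovascular adjudication state no cohort or route split. The gap is confined to TEAE, SAE and AESI incidence and the overview.

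**The contrast with other tables is limited.** The PK summaries are "stratified by cohort, route of administration (IM or IV) and weight categories (1, 2, 3, 4 and all"). There the final level pools weight categories within cohort and route, so it is not an all-participants row. Disposition is the clear example of an overall level.

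**There is a reason to show cohorts separately.** Because of protocol 8.1.1, a pooled TEAE percentage mixes two recording rules. This stands. It argues for keeping the cohort rows and adding a caveat, not for omitting the total. Serious symptoms are recorded in both cohorts, so SAEs are less affected.

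**No precision target is missed.** The study is descriptive, and protocol 9.2 rests the 100 on regulatory feedback with no stated interval width. That is correct: the point is avoidable loss of precision, not a failed criterion.

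**Conclusion.** The point holds as a gap in specification. For the incidences that lead the safety assessment, and for the overview, the SAP sets out cohort-by-route results and names no all-participants row, although the sample size was argued on the total.

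Followed literally, the tightest planned zero-event bound depends on an undocumented split. The pooled limit is 7.7%. The limit is at least 28.5% in the smallest cell if all four are occupied, and about 15% if there are two cells of about 23. The four-cell bound assumes only that each cell has at least one child; the two-cell figure assumes a near-even split.

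A reader might also infer that every cell is very small, or that the layout makes the study less likely to detect an event. Neither follows. No cell sizes are given, and an event in any of the 46 children would still appear in some cell. What is missing is the pooled incidence and its interval.

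**What to change.** In SAP 4.2.2.1, specify for TEAEs, SAEs, AESIs and the overview:
1. an all-participants row, then all-IM and all-IV rows across cohorts, each with n, percentage, exact 95% interval, number of events and exposure-adjusted rate, on the SAF;
2. the existing cohort-by-route rows, kept beneath them;
3. a note beside the pooled TEAE figure that COVID-19 symptoms are recorded as adverse events under different rules in Cohort 1 and Cohort 2 (protocol 8.1.1).

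Reconcile SAP 4.2.2, which names the SES, with SAP Table 2, which names the SAF. Without this, the new row need not contain all 46. If the table shells already hold these rows, the SAP sentence only has to say so.

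The cost is some SAP wording, a few extra rows or columns, and a pooled TEAE percentage that must carry its caveat. No new data or hypothesis test is needed. A further split by age group is not part of this change: SAP 4.2.2.6 plans no safety subgroup analyses, and it would create more small cells.

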#### **4.2.2.2      Laboratory parameters**

Hematology, clinical chemistry, coagulation, and urinalysis parameters will be summarized quantitatively by count, mean, SD and median, and listed by visit and cohort together with their changes from baseline.

The listings will include the following information: test name, date of measurement, reference range, result and flags for any measurements that are outside the reference range (eg, AstraZeneca, program, or laboratory ranges) and include repeat or unscheduled measurements. Clinical laboratory data will be reported in System International units.

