## AMENDMENT HISTORY

Category Change refers to:	Date	Description of change	In line with Clinical Study Protocol?	Rationale
Data presentation	26-Oct-2022	Removed reference to PK data for DSMB	Yes	Updated protocol
Other	26-Oct-2022	Minor text corrections	N/A	Typos and consistency
Data presentation	26-Oct-2022	Removed summary of AEs by maximum intensity	No	Sponsor request per AZD7442 program-level shell changes
Data presentation	26-Oct-2022	Added confidence intervals for percentage of subjects with AEs	Yes	Sponsor request per AZD7442 program-level shell changes
Data presentation	26-Oct-2022	Clarified ECG evaluation summary to be a shift table	Yes	Clarification of presentation per AZ standard shell
Other	26-Oct-2022	Demographics: correction of estimated gestational age for prematurely born infants at birth, not study entry	Yes	Correction
Data presentation	26-Oct-2022	COVID-19 incidence will be summarized by weight categories, and route of administration, not by dose	Yes	Correction. This is a single-dose study
Other	26-Oct-2022	ADA Evaluable Analysis Sets have been clearly distinguished, defining one set each for AZD1061, AZD8895, AZD7442	Yes	Clarification
Other	26-Oct-2022	Mis-assignment to Cohort 1 via contradictory rapid and confirmatory COVID-19 test handling explained. Added separate analysis set and repetition of COVID-19 incidence summary for this set.	Yes	Newly identified potential case of erroneous cohort assignment
Statistical analysis method for secondary endpoint(s)	26-Oct-2022	The SARS-CoV-2 viral loads will be log10-transformed before summary.	Yes	Clarification on result presentation

CATEGORY Change refers to:	Date	Description of change	In line with Clinical Study Protocol?	Rationale
Statistical analysis method for secondary endpoint(s)	26-Oct-2022	Time-to-Event summaries will include quartiles.	Yes	Addition of statistic
Other	26-Oct-2022	Clarification of vaccinations status as captured in the eCRF at baseline.	Yes	Clarification of definition
Other	26-Oct-2022	Description of use of unscheduled and repeated assessments added.	Yes	Addition of information
Data presentation	26-Oct-2022	Presentation of descriptive statistics: quartiles, minimum, maximum updated for several variables and explicitly stated where applicable.	Yes	Sponsor request per AZD7442 program-level shell changes
Other	30-May-2023	Updated information on cohorts and early stop of recruitment.	Yes	Early discontinuation of patient recruitment

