## **3.3 General Considerations**

### **3.3.1 General Study Level Definitions**

All original and derived parameters as well as demographic and disposition data will be listed and described using summary statistics. All safety data (scheduled and unscheduled) will be presented in the data listings.

Summaries will be based on the visit schedule, but unscheduled and repeated assessments captured will be used for definition of baseline or for identification of worst post-baseline evaluations. If there is an unscheduled and a scheduled assessment with the same date, the unscheduled assessment will be assumed to be a repetition and the scheduled result used for summaries.

Frequency counts (number of participants [n] and percentages) will be produced for each qualitative variable. Descriptive statistics (n, mean, SD, median, minimum and maximum) will be calculated for each quantitative variable (unless otherwise stated). Descriptive statistics will only be presented if  $n > 3$ . If no participants have data at a given time point,  $n = 0$  will be presented. If  $n < 3$ , only the n, minimum and maximum will be presented, and if  $n = 3$ , only the n, median, minimum and maximum will be presented; the other descriptive statistics will be left blank.

The CI to a geometric mean will be determined by log-transforming the observations, calculating the 95% confidence limits to the arithmetic mean of the transformed data and back-transforming the confidence limits with the exponential function.

Percentages will be presented to one decimal place. Percentages will not be presented for zero counts. Percentages will be calculated using n as the denominator. The denominator should be clearly presented in each table.

Rounding should be the last operation in the treatment of data. There should be no rounding of intermediate results during the calculation of any derived value. Zeros at the end of a number should be retained.

All statistical analyses and production of tables, figures, and listings will be performed using SAS® version 9.4 or higher. All other requirements and specifications for programming and presentation of TFLs will be specified in the TFL shells document.

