#### 4.2.2.3 Vital Signs

The results of heart rate, respiration rate, pulse rate, pulse oximetry, BP, and body temperature measurements will be listed by participant and time point including the date/time of the assessment, changes from baseline and repeat/unscheduled measurements.

Descriptive statistics (count, mean, SD and median) will be presented by time point for both observed values and changes from baseline.

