#### **4.2.2.5 ECG**

12-lead ECG results will be listed for each participant with overall evaluation by the investigator as Normal, Abnormal or Borderline including clinical significance (CS or NCS).

These evaluations will be summarized via a shift table showing the frequencies and percentages of the baseline evaluation versus the worst post-baseline overall evaluation.

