#### **4.2.2.6 Subgroup Analyses**

No analyses for a specific subgroup are planned.

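### SAP laboratory and vital-sign summary tables give only count, mean, SD and median across all ages, with no extremes, no age or weight strata and no shift or out-of-range counts

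*SAP*

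**What the plan says.** SAP Table 2 places laboratory parameters and vital signs under the primary safety objective. How they are tabulated is set out as follows.

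- **Laboratory (SAP 4.2.2.2):** "Hematology, clinical chemistry, coagulation, and urinalysis parameters will be summarized quantitatively by count, mean, SD and median, and listed by visit and cohort", together with changes from baseline. The listings show the reference range and "flags for any measurements that are outside the reference range", including repeat and unscheduled results. The ranges are described only by example, as sponsor, programme or laboratory ranges.
- **Vital signs (SAP 4.2.2.3):** "Descriptive statistics (count, mean, SD and median) will be presented by time point for both observed values and changes from baseline". No cohort or age split is named, and the listing has values and changes but no range or flag.
- **General default (SAP 3.3.1, matched in protocol 9.4.1):** "Descriptive statistics (n, mean, SD, median, minimum and maximum) will be calculated for each quantitative variable (unless otherwise stated").
- **ECG (SAP 4.2.2.5):** "These evaluations will be summarized via a shift table" of baseline against worst post-baseline evaluation.
- **Subgroups (SAP 4.2.2.6):** "No analyses for a specific subgroup are planned". SAP section 5 mentions age-group display only for the interim analysis, and only as an option.
- **Unscheduled results:** SAP 3.3.7.1 leaves them out of by-visit summaries. SAP 3.3.1 allows them to be used to find the worst post-baseline evaluation.
- **Analysis set:** SAP Table 2 gives the SAF for these endpoints. The text of SAP 4.2.2 bases the summaries on the SARS-CoV-2 nAb Evaluable Analysis Set (SES).

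**The concern.** The purpose of a laboratory or vital-sign table in a 46-participant paediatric study is to show whether any child became abnormal, how many did, and at what age. Four central-tendency and spread statistics, taken over all ages together, do not answer those questions. Normal values for heart rate, blood pressure, creatinine, ALP and haemoglobin differ between infancy and adolescence, so an observed-value table mixes different norms. A minimum, a maximum or a count of out-of-range values would expose an individual; none is planned.

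The adverse-event route does not fully replace these tables. Protocol 8.3.7 restricts adverse-event reporting of test deteriorations because the results are to be summarised in the study report. Only those that are serious, cause discontinuation of the product or are judged clinically relevant become events. The protocol therefore relies on the summaries to carry the rest. The adverse-event tables are by cohort and route, not age (SAP 4.2.2.1), and the summary by maximum intensity has been removed (SAP section 2).

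**Working it through.** The plan gives no figure to reproduce and tests no hypothesis. The check is first textual, then illustrative.

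**Text**

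1. The general default includes minimum and maximum but yields to specific wording. SAP 4.2.2.2 and 4.2.2.3 each give a shorter list, so on a plain reading the extremes are not produced. The amendment history ("Presentation of descriptive statistics: quartiles, minimum, maximum updated for several variables and explicitly stated where applicable") is consistent with choices made variable by variable; I use it only as context.
2. SAP 3.3.1 has a rule for worst post-baseline values, but neither section defines a table that uses it. ECG does.
3. Because the laboratory and vital-sign tables are by visit or time point, SAP 3.3.7.1 removes unscheduled results from them. A repeat sample that confirms an abnormality would not enter the summary.
4. The SES requires a quantifiable post-dose nAb titre (SAP Table 1). Neonates give only safety and PK samples (protocol 8.5.1), so they cannot enter it. Under SAP Table 2 they would be in these tables; under the text of SAP 4.2.2 they would not.

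**Illustration 1: one child (all values assumed except 46)**

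One of 46 children (full analysis set, SAP section 2) has ALT rising from 25 to 400 U/L; the other 45 have zero change.

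- Mean change = (400 − 25)/46 = 375/46 ≈ 8.2 U/L.
- Median change = 0.
- SD of change = √[375² × (1 − 1/46)/45] = 375/√46 ≈ 55 U/L.

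**Illustration 2: general form**

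One child lies k SD from the mean of the other n − 1, whose mean is 0 and SD is 1. The mean becomes k/n, and the SD becomes √{[(n − 2) + k²(1 − 1/n)]/(n − 1)}. The median comes from normal quantiles. For k = 5 (assumed):

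| n | Mean | SD | Median | Maximum |
|---|---|---|---|---|
| 46 | 0.11 | 1.23 | 0.03 | 5 |
| 31 | 0.16 | 1.33 | 0.04 | 5 |
| 21 | 0.24 | 1.46 | 0.06 | 5 |
| 10 | 0.50 | 1.84 | 0.14 | 5 |

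The sizes 31 and 21 are the planned Cohort 1 and 2 minima in protocol Table 5 (19 + 12 and 14 + 7); 10 is a small table for comparison. The actual cohort split of the 46 is not given.

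The mean and median barely move in the larger tables. The SD does react, but it does not say which child, age or direction is involved. The maximum or a shift count shows the child directly.

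**The case against.** The strongest reply is that the safety analysis as a whole does show abnormal children. Protocol 9.4.4 and SAP 4.2.2.1 assess safety primarily through adverse-event incidence. Laboratory listings flag every out-of-range value, and with 46 children such listings can be read case by case. Serious or clinically relevant deteriorations become adverse events. A marked ALT rise such as the one illustrated would, on an assumed upper limit of about 40 U/L, exceed three times that limit and trigger a central-laboratory alert (protocol Appendix D). SAP 3.3.1 also leaves presentation detail to a shells document that is not available here.

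Much of this stands, and it rules out several stronger readings a reader might take:

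- **That an abnormal child would go unseen.** Not supported. The gap is in the laboratory and vital-sign summary tables; listings, adverse events and liver alerts remain.
- **That the ranges are not age-specific.** Not supported. The SAP is silent. The converse, that suitable age-specific flags already exist, is not established either.
- **That the tables reflect the age mix rather than the drug.** This holds at most for observed values. With assumed heart rates of 140, 110, 88 and 75 bpm, group sizes 8, 9, 9 and 20, and a within-age SD of 11, the pooled SD is about 27, or 2.4 times the within-age SD. The planned change-from-baseline tables remove most of that; drift with growth remains but cannot be sized from the documents.
- **That neonates are pooled with 17-year-olds.** This is so only under the SAF, and only if neonates were enrolled.

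What the reply does not meet: listings give no counts or denominators, vital-sign listings have no flag, and the SAP text itself specifies the shorter list of statistics.

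**Conclusion.** The point holds as a limited and inexpensively corrected weakness in presentation. For two components of the primary safety endpoint, the SAP specifies summaries that omit extremes, strata and out-of-range counts and leave unscheduled results out of by-visit tables. It does so although its own default includes minimum and maximum and its own ECG section uses a shift table. In the assumed ALT case, the mean change moves by about 8 U/L, the median by about 0, and the SD of change to about 55 U/L. The dilution is smaller in smaller tables. The conclusion does not depend on those assumed values; it depends on the listed statistics being the complete set, as SAP 4.2.2.2 and 4.2.2.3 read.

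**What to change.** 1. Restore minimum and maximum in the laboratory and vital-sign tables.
2. State that laboratory reference ranges are age- and sex-appropriate.
3. For laboratory parameters, add a low/normal/high shift table from baseline to worst post-baseline value, or out-of-range counts. Include unscheduled results under the worst-value rule in SAP 3.3.1. Show it overall and by age or weight category. The ECG table is a model for the shift format, though it is not itself split by age.
4. Do the same for vital signs once age-appropriate ranges have been specified; the SAP has none at present.
5. Base these tables on the SAF, and reconcile the text of SAP 4.2.2 (SES) with SAP Table 2 (SAF), so that neonates are not lost.

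The cost is a few more descriptive tables, plus the work of specifying vital-sign ranges. Some cells will be small. SAP 3.3.1 curtails statistics when n is 3 or fewer, so in sparse strata counts against an age-appropriate range will be more useful than means.
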